5.0 Inclusion and Exclusion Criteria/ Study Population

Twenty participants with upper extremity post-stroke pain of all ethnic and racial categories will be accepted into this study protocol. No preference will be given based on race, gender, or ethnicity. Pregnant females and children under the age of 18 will be excluded for safety reasons.

Inclusion Criteria:

- Age 18-80
- Have the capacity and ability to provide one’s own consent in English and sign the informed consent document.
- Ischemic or hemorrhagic stroke that occurred at least 6 months prior
- Unilateral stroke lesions in the left hemisphere
- Right upper extremity pain

Exclusion Criteria:

- Primary intracerebral hematoma or subarachnoid hemorrhage
- Documented history of dementia

- Documented history of uncontrolled depression or psychiatric disorder
- Uncontrolled hypertension despite treatment, specifically SBP (Systolic Blood Pressure) / DBP (Diastolic Blood Pressure) $\geq 180/100$ mmHg
- Pregnancy

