10.0 Study Design / Methods

Study Overview:

After determining eligibility and interest, written informed consent will be obtained from participants at the MUSC Center for Biomedical Imaging. After consent is obtained, the participants will then complete a pregnancy test and conduct a brief daily life functioning battery. Enrolled participants will start the experiment. They will first finish the subjective pain rating and have quantitative sensory testing (QST) conducted to determine baseline pain thresholds. Participants will then receive 30 minutes of tVNS (either active or sham). Upon the completion of the stimulation intervention, they will then be tested for another subjective pain rating and QST. The timeline of the experiment and group assignment overview are displayed below.

Experiment Overview – Investigate the anti-pain effect of taVNS in chronic post-stroke upper extremity pain

Recruitment, Screening, and Consent Procedures:

Recruitment will be conducted by the study team utilizing the MUSC RESTORE list to identify and contact prospective chronic stroke patients. Participants who are found to be appropriate candidates will be offered to be phone screened and educated regarding the study's details. If interested in participating in the study, they will be consented and enrolled into the study's protocol. Additionally, RESTORE staff can also give rack cards to interested RESTORE (stroke registry) individuals. If interested in participating in the study, they will be consented and enrolled into the study's protocol.

Daily Life Function Battery:

All participants will complete a daily life function battery after being enrolled. This battery includes the following questionnaires in specific life domains that will be used to identify baseline characteristics of individuals: Demographics; Pain Screening; Substance Use: TAPS; Pain Intensity & Interference: PEG; Physical Functioning/QDL: PROMIS Physical Functioning 6b; Sleep: PROMIS Sleep Disturbance 6a; Sleep: Sleep Duration; Depression: PHQ9; Anxiety: GAD7.

Pregnancy Test Procedures:

If participants are a person of childbearing age, they will be provided with a pregnancy test strip. After completing the pregnancy test, participants with negative results will be asked to continue to the remaining study procedures, whereas those with a positive result will be debriefed and released.

Subjective Pain Rating:

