channels of stimulation (auricular vagus, auricular trigeminal, and both). Two individual stimulation frequencies will be set: 15 Hz at cymba concha and 100 Hz adjacently anterior to tragus. The pulse duration will be set to 250 μ s for all participants. The stimulation intensities delivered (in mA) will be a standardized 2X Perceptual Threshold. This means that all individuals will first have a perceptual threshold conducted, during which incremental increases and decreases in current intensity will be applied until the participant barely feels the stimulation. That is considered the perceptual threshold. All stimulation then will be delivered at 2X this value. Perceptual threshold will be conducted at the beginning of the taVNS intervention. This is how we have conducted stimulation at MUSC in prior IRB-approved studies which have been safe and rated comfortable and not painful. Sham stimulation will be administered at identical parameters of cymba concha, however, the electrodes will be attached to the earlobe, which is not believed to have a high density of cranial nerve innervation. If the participant states that the stimulation intensity is discomforting or imperceivable in any of the stimulation groups, the researcher will gradually decrease until a comfortable stimulation intensity is achieved. The taVNS session will last for 30 minutes.

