14.0 Withdrawal of Subjects

Participants will be informed during consenting that they are free to withdraw from the study at any time. They will be informed that they are not obligated to participate once the study is initiated and in particular will be reminded prior to taVNS/VNS stimulation they may discontinue stimulation and/or the experiment at any point. taVNS has been a very safe procedure and we do not anticipate subject withdrawal due to taVNS side effects. No participants in previous studies utilizing taVNS have been forced to withdraw for medical or physiological purposes, and we do not anticipate any issues during this study. If participants begin to experience ear pain, an attempt can be made on the other ear, as well as a reduction in the intensity of stimulation before termination would be required. We will be monitoring the stimulation session and if a patient is extremely sensitive to the device we might consider terminating. In that case, the participant and their guardian would be informed of the need for termination.

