15.0 Risks to Subjects

Ear Stimulation:

Ear stimulation is safe, however, there are some risks associated with stimulating the ear: There may be local discomfort. This will likely be temporary. In extreme cases, burns might occur. We will monitor any potential burns via direct communication with participants and will stop stimulation and advise subjects to apply vitamin E cream. The tissue surrounding the ear may be sensitive, sore, or feel slight numbness. Hopefully, this will be temporary and will go away after the stimulation is turned off.

Safety in Case of Pregnancy:

This protocol will exclude pregnant women. The risks of using taVNS with pregnant women are currently unknown. If in the screening and consent a patient is a woman of childbearing age, they will be tested prior to receiving any taVNS.

Potential Headache, Dizziness, and Facial Pain:

Ear stimulation might cause headaches or face pain, which should resolve shortly after treatment.

Potential Decrease in Heart Rate:

Ear stimulation may slow heart rate. In rare cases (less than 1%) decreased blood pressure or fainting may occur. We expect no significant changes in heart rate or blood pressure, or fainting to occur. For the initial sessions, all subjects will be stimulated while they are seated, never standing. We expect no significant changes in heart rate or blood pressure, but if this occurs, the study team will evaluate the situation and either decide that the patient should be dropped from the study, or do all sessions lying on a couch, or with lower doses.

QST Pain Assessments:

The Medoc pain assessment system has been used safely by Co-I [name] and others for over a decade now. The pain is unpleasant but there are limits to the amount of pain, and there have been no adverse events over 5 prior MUSC IRB-approved pain studies using this approach. Some participants may report feeling anxious before experiencing a painful stimulus, however, this is rare and if occurs, the participant will be able to request to stop voluntarily.

Unknown Risks:

There is always the possibility of other risks for a relatively new technology. The Study team will let the participant know if they learn anything that might make the participant change their mind about participating in the study.

Loss of Confidentiality:

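### Section 15.0 ties action to significant changes in heart rate or blood pressure, but no written visit step measures either, so symptom-free changes would go unrecorded

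*Protocol*

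**What the plan says.** The relevant text is in four places in the protocol.

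- **Risk and response (Section 15.0, Potential Decrease in Heart Rate).** The risk is stated as "Ear stimulation may slow heart rate. In rare cases (less than 1%) decreased blood pressure or fainting may occur". The response follows: "We expect no significant changes in heart rate or blood pressure, but if this occurs, the study team will evaluate the situation". The options are to "either decide that the patient should be dropped from the study, or do all sessions lying on a couch, or with lower doses". The paragraph does not say what makes a change significant or how it would be noticed.
- **Visit (Section 10.0).** After consent, "the participants will then complete a pregnancy test and conduct a brief daily life functioning battery". A pain rating and quantitative sensory testing (QST) come next, then stimulation. The one measurement described at the start of stimulation is this: "Perceptual threshold will be conducted at the beginning of the taVNS intervention". Afterwards: "Upon the completion of the stimulation intervention, they will then be tested for another subjective pain rating and QST".
- **Monitoring (Section 14.0).** "We will be monitoring the stimulation session and if a patient is extremely sensitive to the device we might consider terminating".
- **Outcome (Section 4.0).** Safety and feasibility form the primary outcome.

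Elsewhere, blood pressure appears only as an exclusion criterion in Section 5.0, for uncontrolled hypertension at 180/100 mmHg or above.

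**The concern.** A change can be seen only by comparing a reading with an earlier one. Section 15.0 makes such a change the trigger for team evaluation and possible removal, yet the written visit produces neither reading. Staff who follow the text can act on what they see or are told. They cannot act on a slower pulse or lower pressure that causes no symptoms.

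What is at stake is the primary outcome. The protocol expects no significant change in heart rate or blood pressure. If nothing is measured, the final report could repeat that expectation as a result, and a reader could not tell a true absence from a failure to look. A later, larger trial would inherit that gap in the safety record.

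This does not belong to a statistical analysis plan. Which readings are taken at the visit is fixed by the protocol, and an analysis plan cannot summarise values that were never collected.

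**Working it through.** The protocol states no figure on this point, so there is nothing to reproduce. The check sets the trigger beside each place where a reading could occur.

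**What the trigger needs.** (a) A baseline value of heart rate or blood pressure. (b) At least one later value, during or after stimulation. (c) A rule for when the difference counts as significant.

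**What the written text supplies.**

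| Place in the protocol | What is obtained | Heart rate or blood pressure? |
|---|---|---|
| 5.0, exclusion criteria | A 180/100 mmHg cut-off, source of the value not stated | Cut-off only, no measurement step |
| 10.0, daily life function battery | Demographics, pain screening, and questionnaires on substance use, pain interference, physical function, sleep, depression and anxiety | No |
| 10.0, pregnancy test | Test strip | No |
| 10.0, pain rating and QST, before | 0-10 rating and thermal thresholds | No |
| 10.0, taVNS procedures | Perceptual threshold, and intensity adjusted on reported discomfort | No |
| 10.0, pain rating and QST, after | 0-10 rating and thermal thresholds | No |
| 13.0, safety monitoring | Reporting of any adverse event within 48 hours | No |
| 14.0, withdrawal | Session monitored, in the context of ear pain and sensitivity to the device | Not stated |
| 15.0, ear stimulation | Burns followed by talking with the participant | No |

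Items (a) and (b) are supplied by no written step, and item (c) is not defined anywhere.

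**Comparison with other risks.** The protocol does attach a means of detection to some risks: a test strip for pregnancy, and direct communication for burns. Communication suits a burn, which the participant can feel. It does not suit a fall in pulse or pressure that the participant may not feel.

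**Effect on the comparison of arms.** The electrodes sit at different sites in the two arms (tragus and cymba conchae, or earlobe), so staff who place or watch them can tell the arm. Observation without a fixed reading could therefore be more attentive in one arm than in the other. Identical readings in both arms reduce that risk.

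**The response text.** Section 1.0 describes a single-visit trial, and the taVNS procedures in Section 10.0 describe one 30-minute session. The Section 15.0 paragraph speaks of initial sessions, seated, and offers changes that would apply to all sessions. With one session there are no further ones to which those options could apply, so part of the stated response does not fit the design.

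**The case against.** The strongest reply is that the protocol does not leave the participant unwatched. Section 14.0 says the session is monitored, participants may stop at any point, and intensity is lowered on reported discomfort. All of this stands. It rules out an inference that a reader might draw, namely that only a visible collapse could prompt action. The documents do not support that: the trigger is any significant change, and a complaint short of fainting can reach the team. What remains is that the monitoring has no stated content and mentions no pulse or pressure reading.

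Three other stronger readings are also unsupported.

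- A reader might call this the only systemic risk named for the device. Section 15.0 also lists dizziness and headache under their own heading, and dizziness is a symptom the participant can report.
- A reader might conclude that the 180/100 mmHg exclusion cannot be applied. The value could come from records or from screening. Such a value would not show a change during stimulation, so the exclusion neither causes nor cures the gap.
- A reader might use the stated frequency of under 1% to size the problem. That figure concerns lowered pressure or fainting. Fainting needs no instrument to notice, and the protocol gives no frequency for symptom-free changes, so a probability built on it would not measure this defect.

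Finally, Section 10.0 refers to a displayed timeline that is not visible in the text reviewed. It might show vital signs. The written steps are detailed and mention none, so this lowers certainty without removing the point.

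**Conclusion.** The point holds in a limited form. The protocol names a cardiovascular risk and ties action to changes in heart rate or blood pressure, but the written procedures give no means of observing such a change unless it produces symptoms or is noticed by chance. Ascertainment of this part of the primary safety outcome is incomplete for all 20 planned participants, in both arms.

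The size is best stated as a count: no heart rate or blood pressure reading in the written visit, where at least two (one baseline, one later) are needed to show a change. How many changes would be missed cannot be estimated from the document.

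The conclusion assumes that the unseen timeline figure adds no such reading and that the monitoring in Section 14.0 means no more than it says. Confidence is therefore moderate. The point deserves a change to the protocol, because a stated trigger cannot be observed as written and the remedy is cheap. It does not show that participants are unmonitored.

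**What to change.** 1. Reconcile Section 15.0 with Section 10.0 by adding heart rate and blood pressure readings at baseline and around the stimulation session, taken in the same way in both arms by staff already present.
2. Record the values under the primary safety outcome in Section 4.0, so that any statement about changes rests on data.
3. Have the investigators state in advance the timing of the readings, what counts as significant, and the response. These are clinical decisions and none is proposed here.
4. Reconcile the wording about initial sessions and all sessions in Section 15.0 with the single-visit, single-session design.
5. If the timeline figure already shows such readings, carry them into the text.

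The cost is a short amendment and a few minutes per visit, with no extra staff and no invasive procedure. The downside is small: more minor fluctuations will be recorded and will need to be reported with the definition set under step 3.

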16.0 Potential Benefits to Subjects or Others

There will be no direct benefit to the participant in the study. Data from this study, however, will benefit society by improving the understanding of if and how tAVNS controls pain and potentially work towards developing a novel therapeutic device.

17.0 Sharing of Results with Subjects

There is no plan to inform subjects of the results of the study, but they can always contact the research staff and ask. If there are significant new findings during the course of the study, they will be notified.

18.0 Drugs or Devices

tAN Device (Spark Biomedical Sparrow Ascent)

tAN has been determined a non-significant risk determination of this device. We are using the Spark Sparrow Ascent tAN system outlined in this document, based on the FDA-cleared Sparrow System (K201873). IRB 1 has consistently given NSR status for all prior tAVNS studies at MUSC, including studies in stroke patients ([name]), brain damaged newborns learning to feed ([name], [name]), Parkinson's Disease ([name], [name]) and healthy volunteers ([name], [name]).

QST Pain Device (Medoc Pathway TSA2)

Medoc's TSA2 offers thermal stimulation in the full range from sensation to pain, in heat and cold, using one or two thermodes simultaneously. A wide variety of thermodes is available for each body site or stimulation profile. Excellent temperature control and fast rates make the device accurate, the test repeatable, and suitable for a great number of applications. Medoc has been developing and manufacturing QST devices in the thermal, pressure, and vibratory modalities for over 30 years. This system has been IRB-approved here at MUSC in prior work conducted by the Co-Is ([name], [name]).

References

BADRAN, B. W., PENG, X., BAKER-VOGEL, B., HUTCHISON, S., FINETTO, P., RISHE, K., FORTUNE, A., KITCHENS, E., O'LEARY, G. H. & SHORT, A. 2023. Motor Activated Auricular Vagus Nerve Stimulation as a Potential Neuromodulation Approach for Post-Stroke Motor Rehabilitation: A Pilot Study. *Neurorehabilitation and Neural Repair*, 15459683231173357.

BAO, S.-C., KHAN, A., SONG, R. & TONG, R. K.-Y. 2020. Rewiring the lesioned brain: electrical stimulation for post-stroke motor restoration. *Journal of stroke*, 22, 47.

BITTAR, R. G., KAR-PURKAYASTHA, I., OWEN, S. L., BEAR, R. E., GREEN, A., WANG, S. & AZIZ, T. Z. 2005. Deep brain stimulation for pain relief: a meta-analysis. *Journal of clinical neuroscience*, 12, 515-519.

